3.3.2 Exclusion Criteria

Subjects will be ineligible for this study if they meet **any** of the following criteria:

1. Prior malignancy (other than lung cancer), except for adequately treated basal cell or squamous cell skin cancer, in situ cancer, or other cancer from which the subject has been disease free for \geq 2 years.
2. Known central nervous system metastases and/or carcinomatous meningitis. Brain metastases, but not carcinomatous meningitis, are allowed if they had been previously treated (either surgically resected or by radiation therapy) and had remained stable by repeat imaging \geq 4 weeks after treatment before enrolling on this protocol.
3. Significant cardiovascular disease such as uncontrolled or symptomatic arrhythmias, congestive heart failure, or myocardial infarction within 6 months of screening, or any Class 3 or 4 cardiac disease as defined by the New York Heart Association Functional Classification, or corrected QT interval (QTc) $>$ 480 msec at screening.
4. Malabsorption syndrome, disease significantly affecting gastrointestinal function, or resection of the stomach or small bowel, symptomatic inflammatory bowel disease, partial or complete bowel obstruction, or gastric restrictions and bariatric surgery, such as gastric bypass.
5. Prior therapy with any inhibitor of BTK, AKT, JAK, mTOR, PI3K, or SYK.
6. Prior therapy with an anti-PD-1, anti-PD-L1, anti-PD-L2, anti-CD137, or anti-CTLA-4 antibody (including ipilimumab, tremelimumab, nivolumab, pembrolizumab, MPDL3280A or any other antibody or drug specifically targeting T-cell co-stimulation or checkpoint pathways).

7. Receiving ongoing immunosuppressive therapy, including systemic or enteric corticosteroids except for non-systemically absorbed treatments (such as inhaled or topical steroid therapy for asthma, chronic obstructive pulmonary disease, or allergic rhinitis) within 7 days before the first dose of pembrolizumab.
8. Active autoimmune disease that has required systemic treatment in past 2 years (ie, with use of disease modifying agents, corticosteroids or immunosuppressive drugs). Note: Replacement therapy (eg, thyroxine, insulin, or physiologic corticosteroid replacement therapy for adrenal or pituitary insufficiency) is not considered a form of systemic treatment.
9. Has evidence of active, non-infectious pneumonitis or a history of interstitial lung disease.
10. History of severe allergic, anaphylactic, or other hypersensitivity reactions to chimeric or humanized antibodies or fusion proteins.
11. History of bleeding diathesis (eg, hemophilia or von Willebrand disease).
12. Requires treatment with a strong CYP3A inhibitor/inducer.
13. Requires or receiving anticoagulation with warfarin or equivalent vitamin K antagonists (eg, phenprocoumon) within 7 days of first dose of study drug.
14. Requires treatment with proton-pump inhibitors (eg, omeprazole, esomeprazole, lansoprazole, dexlansoprazole, rabeprazole, or pantoprazole).
15. Known history of HIV or active infection with HCV or HBV, or any active infection requiring systemic therapy within 2 weeks before first dose of study drug. Note: Subjects receiving prophylactic antibiotics (eg, for prevention of a urinary tract infection or chronic obstructive pulmonary disease) are eligible.
16. History of stroke or intracranial hemorrhage within 6 months before the first dose of study drug.
17. Major surgical procedure within 28 days of first dose of study drug. Note: If a subject had major surgery, they must have recovered adequately from any toxicity and/or complications from the intervention before the first dose of study drug.
18. Prior allogeneic bone marrow transplantation or prior solid organ transplantation.
19. Has received a live vaccine within 30 days of planned start of study therapy.
20. ANC $< 1.5 \times 10^9/L$ or platelet count $< 100 \times 10^9/L$ or hemoglobin $< 8.0 \text{ g/dL}$.
21. Total bilirubin $> 1.5 \times \text{ULN}$; and AST or ALT $> 3.0 \times \text{ULN}$.
22. Estimated creatinine clearance of $< 30 \text{ mL/min}$, calculated using the formula of Cockroft and Gault $(140 - \text{Age}) \cdot \text{Mass (kg)} / (72 \cdot \text{creatinine mg/dL})$; multiply by 0.85 if female.
23. Breastfeeding or pregnant or expecting to conceive or father children within the projected duration of the trial, starting with the screening visit through 120 days after the last dose of trial treatment.
24. Is currently participating in a clinical trial and receiving study therapy or has participated in a study of an investigational agent and received study therapy or used an investigational device within 4 weeks of the first dose of treatment.
25. Immediate family members of the sponsor personnel or site staff directly involved with the conduct of this protocol are excluded from participating on this study.
26. Presence of a gastrointestinal ulcer diagnosed by endoscopy within 3 months prior to screening.
27. Serologic status reflecting active hepatitis B or C infection. Subjects with hepatitis B core antibody positive who are surface antigen negative or who are hepatitis C

antibody positive will need to have a negative PCR result before enrollment. Those who are hepatitis B surface antigen positive or hepatitis B PCR positive and those who are hepatitis C PCR positive will be excluded.

3.3.3 Replacement of Subjects

Subjects will not be replaced on this study except if needed to complete the DLT assessment (N=6). However, subjects who discontinue from the study due to a DLT during the DLT assessment period will not be replaced.

3.3.4 Enrollment and Randomization Procedures

Enrollment of a subject into the study will be performed according to the following procedure:

The study center will notify the sponsor when a clinically eligible subject is identified and is ready to screen, to ensure enrollment availability on the study.

After the subject has signed and dated the Informed Consent Form (ICF), all screening procedures have been completed, and eligibility has been confirmed, the subject can be officially enrolled into the study.

To enroll a subject, the study center will fax/email a completed Enrollment Confirmation Form to the sponsor. The enrollment date will be the date that the sponsor confirms enrollment. The sponsor will aim to fax/email a completed Enrollment Confirmation Form to the study center within 24 hours.

The treatment assignment is based on the randomization list generated by the sponsor before study enrollment begins.

The Enrollment Confirmation Form will contain treatment-arm allocation.

Treatment must begin within the screening window ([Section 4.1](#)) and after the site has received the treatment-arm allocation from the sponsor.

3.4 STUDY DRUGS

3.4.1 Premedications

No specific premedications or supporting medications are required in conjunction with acalabrutinib or pembrolizumab administration.

3.4.2 Formulation, Packaging, and Storage

Acalabrutinib

Acalabrutinib is manufactured according to cGMP regulations and will be provided to the investigational site by Acerta Pharma or designee. Acalabrutinib should be stored according to the instructions on the label that is affixed to the package of the drug product. Acalabrutinib will be provided in white, high-density polyethylene bottles.

If a drug shipment arrives damaged, or if there are any other drug complaints, a Product Complaint Form should be completed and emailed or faxed to the sponsor or the sponsor's representative. Refer to the Acalabrutinib Investigator Brochure for additional information regarding the drug product to be used in this trial.

Pembrolizumab

Commercially available pembrolizumab (KEYTRUDA) will be provided by the sponsor for use on this study ([Table 3-1.](#)). Pembrolizumab (100 mg/4 mL) is provided as 25-mg/mL solution in single-use vials or as a lyophilized powder for reconstitution (50 mg/vial).

Table 3-1. Pembrolizumab Product Descriptions

Product Name & Potency	Dosage Form
MK-3475 50 mg	Lyophilized Powder for Injection
MK-3475 100 mg/ 4mL	Solution for Injection

Information on the formulation, packaging and storage of pembrolizumab is provided in the package insert ([Appendix 6](#)).

3.4.3 Administration of Study Drug

Investigators are prohibited from supplying acalabrutinib to any subjects not properly enrolled in this study. The investigator must ensure that subjects receive acalabrutinib or pembrolizumab only from personnel who fully understand the procedures for administering the drugs.

Acalabrutinib 100 mg is intended to be administered orally twice daily with 8 ounces (approximately 240 mL) of water (avoid grapefruit juice or Seville orange juice due to potential inhibition of CYP3A). Doses should be administered 12 hours apart (a window of \pm 1 hour is allowed). The capsules should be swallowed intact and subjects should not attempt to open capsules or dissolve them in water.

If a dose is missed, it can be taken up to 3 hours after the scheduled time with a return to the normal schedule the same or following day. If it has been $>$ 3 hours, the dose should not be taken and the subject should take the next dose at the scheduled time the

next day. The missed dose will not be made up and must be returned to the site at the next scheduled visit.

Guidance on co-administration of acalabrutinib with agents that affect gastric pH is provided in [Section 3.10.4](#).

Pembrolizumab will be administered as a dose of 200 mg using a 30-minute IV infusion. Sites should make every effort to target infusion timing to be as close to 30 minutes as possible. However, given the variability of infusion pumps from site to site, a window between -5 minutes and +10 minutes is permitted (ie, infusion time is 30 minutes -5 min/+10 min). Detailed information on preparation of pembrolizumab for infusion is provided in [Appendix 6](#).

When acalabrutinib and pembrolizumab are administered on the same day, acalabrutinib should be administered first, followed by pembrolizumab. When PK sampling is done, the pembrolizumab infusion should begin within 10 minutes of ingesting acalabrutinib.

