3.5.2 Arm 2 – Combination Treatment

The dose of acalabrutinib is 100 mg BID PO. The doses may be modified for DLTs as summarized in [Table 3-2](#).

Pembrolizumab 200 mg will be administered every 3 weeks by IV infusion for a maximum of 24 months from the date of first dose.

Acalabrutinib and pembrolizumab dosing will begin on the same day (Day 1 of Week 1) except for the first 6 subjects enrolled due to PK sampling. The first 6 subjects enrolled will receive acalabrutinib on Day 1 of Week 1. Then on Day 2 of Week 1 the first pembrolizumab infusion will be administered.

Table 3-2. Dose Reduction for Acalabrutinib

Dose Level	Acalabrutinib	Pembrolizumab
Starting Dose	100 mg BID PO	200 mg Q3W IV
Level -1	100 mg QD PO	200 mg Q3W IV
Level -2	50 mg BID PO	200 mg Q3W IV

Abbreviations: BID = twice per day; IV = intravenous, PO = oral; Q3W = every 3 weeks; QD = once per day

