5.4.3 Study Treatment Administration and Compliance

Descriptive information will be provided regarding the number of acalabrutinib and pembrolizumab doses prescribed, the total number of doses taken, the number of days of treatment, and the number and timing of prescribed dose reductions and interruptions.

For each subject, acalabrutinib and pembrolizumab compliance will be described in terms of the proportion of study drug actually taken.

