Appendix 5. Schedule of Assessments – Crossover

Treatment Phase (Weeks)					
Weeks After Crossover ^{a,b}	0	1	2	3	≥ 4
Study Window	± 3 days				
Vital signs		X	X		
Lab assessments:					
Hematology ^c	X	X			
Serum chemistry ^d	X	X			
Study drug compliance	X	X			
Concomitant medications	X	X			
Adverse events	X	X			
Acalabrutinib 100 mg BID ^b	X	X	X	X	
Pembrolizumab 200 mg Q3W	X				X

Abbreviations: BID = twice per day; Q3W = every 3 weeks.

Footnotes for ACE-ST-007 Schedule of Study Activities - Crossover:

- Subjects are to complete assessments as shown in the 2 weeks following crossover. (Eg, if a subject crosses over to receive acalabrutinib and pembrolizumab at Week 10, assessments will be performed as listed for Week 10 in [Appendix 4](#). During Weeks 11 and 12, assessments will be performed as listed above for Weeks 1 and 2 after crossover. During Week 13, assessments will be performed as listed in Week 13 in [Appendix 4](#); assessments will be performed as listed in [Appendix 4](#) for all subsequent weeks).
- Subjects who cross over to receive acalabrutinib in addition to pembrolizumab should start acalabrutinib treatment at the next visit in which they are scheduled to receive pembrolizumab.
- Hematology includes complete blood count with differential and platelet and reticulocyte counts.
- Serum chemistry: albumin, alkaline phosphatase, alanine transaminase (ALT), aspartate aminotransferase (AST), bicarbonate, blood urea nitrogen (BUN), bone-specific alkaline phosphatase, calcium, chloride, creatinine, glucose, lactate dehydrogenase (LDH), magnesium, phosphate, potassium, sodium, total bilirubin, total protein, and uric acid.

Product: Acalabrutinib (ACP-196)

Date: 23 May 2016

Protocol: ACE-ST-007

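### Read literally, the missed-dose rule in Section 3.4.3 turns one missed morning dose of twice-daily acalabrutinib into two omitted doses

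*Protocol*

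**What the plan says.** Section 3.4.3 sets the regimen: "Acalabrutinib 100 mg is intended to be administered orally twice daily", and "Doses should be administered 12 hours apart", with a window of 1 hour either way. Two rules for a late dose follow.

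- **Up to 3 hours late:** the dose may be taken, "with a return to the normal schedule the same or following day".
- **More than 3 hours late:** "the dose should not be taken and the subject should take the next dose at the scheduled time the" and, after the page break, "next day. The missed dose will not be made up and must be returned to the site at the next scheduled visit".

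Neither rule separates morning from evening doses, or twice-daily from once-daily dosing.

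Twice daily is the main regimen. Section 3.5.2 states "The dose of acalabrutinib is 100 mg BID PO". In Table 3-2 the starting dose and Level -2 (50 mg) are twice daily; only Level -1 (100 mg) is once daily. The crossover schedule in Appendix 5 lists "Acalabrutinib 100 mg BID", although Section 3.0 makes the crossover dose depend on the Arm 2 DLT review.

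Section 5.4.3 says that "compliance will be described in terms of the proportion of study drug actually taken".

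**The concern.** On a 12-hourly schedule, the dose after a missed morning dose falls on the same evening. The rule for a skipped dose names only the following day, so a subject who follows it to the letter also omits an evening dose that was never late. The rule for a shorter delay does provide for resuming on the same day; the rule for a skipped dose does not.

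Acalabrutinib is mostly taken at home, so subjects depend on the instruction they are given. If some sites apply the text literally and others infer that the evening dose should be taken, the same event is handled in two ways, and the second departs from the written protocol. At stake is a small, avoidable loss of acalabrutinib exposure in Arm 2 and in crossover subjects on twice-daily dosing.

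The compliance summary in Section 5.4.3 is not distorted: it would correctly show the extra omitted dose as lower compliance.

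**Working it through.** The check is clock arithmetic. The protocol states no figure for this, so there is none to reproduce.

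**Inputs**
- 12-hour interval, 1-hour window either way, 3-hour cut-off: Section 3.4.3.
- Dose levels 100 mg BID, 100 mg QD (Level -1) and 50 mg BID (Level -2): Table 3-2.
- Assumption: nominal dose times of 08:00 and 20:00. The protocol gives no clock times; any pair 12 hours apart gives the same gaps.
- Pembrolizumab interval of 21 days, used only as a convenient denominator.

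**Gap and doses omitted after one dose is missed by more than 3 hours**

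| Case | Last dose taken | Next dose taken | Gap | Doses omitted |
|---|---|---|---|---|
| BID, morning missed, rule as written | Day 0, 20:00 | Day 2, 08:00 | 36 h | 2 |
| BID, morning missed, 12-hourly schedule kept | Day 0, 20:00 | Day 1, 20:00 | 24 h | 1 |
| BID, evening missed, rule as written | Day 1, 08:00 | Day 2, 08:00 | 24 h | 1 |
| QD, dose missed, rule as written | Day 0, 08:00 | Day 2, 08:00 | 48 h | 1 |

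Only the first row departs from the intended schedule.

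**Ranges.** Allowing 1 hour either way at both ends, the gap is 36 ± 2 = 34 to 38 h under the rule, against 24 ± 2 = 22 to 26 h on schedule. If a dose at either end also uses the 3-hour late allowance, the extremes widen:
- Rule as written: 23:00 on Day 0 to 07:00 on Day 2 = 32 h; 19:00 on Day 0 to 11:00 on Day 2 = 40 h.
- Schedule kept: 23:00 on Day 0 to 19:00 on Day 1 = 20 h; 19:00 on Day 0 to 23:00 on Day 1 = 28 h.

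The two ranges do not overlap in either case.

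**Drug omitted**
- Starting dose: 2 × 100 = 200 mg, against 100 mg.
- Level -2: 2 × 50 = 100 mg, against 50 mg.

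**Compliance over 21 days**
- Doses due: 21 × 2 = 42.
- Rule as written: 40/42 = 95.2%.
- Schedule kept: 41/42 = 97.6%.
- Difference: 1/42 = 2.4 percentage points per event.

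**Search for a text that resolves it.** Section 3.4.4 returns missed pembrolizumab doses to their original schedule but has no matching rule for acalabrutinib. Sections 3.5.2 and 3.8 and Appendix 5 do not restore the evening dose.

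**Pharmacodynamics.** Section 1.7.1 reports 91.5% BTK occupancy at 24 hours in the 100-mg single-dose cohort and nothing at 36 hours. The effect of the longer gap on occupancy therefore cannot be derived from the document.

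**The case against.** The strongest reply is that the harm needs a very literal reading. The paragraph fixes dosing at 12-hour intervals, the rule speaks of one missed dose in the singular, and nothing tells a subject in so many words to omit a dose not yet due. Read as a whole, the intention is to skip one dose, and many sites would act on that. This is fair as to intent, but it shows that the instruction departs from its own purpose; it does not make the instruction correct.

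Four smaller points also stand:
- A gap range that uses only the 1-hour window is too narrow once the 3-hour allowance is counted; the wider range is given above and leaves the conclusion unchanged.
- Crossover subjects are affected only if the DLT review leaves them on a twice-daily dose.
- Section 3.4.4 describes the diary as a record of dose times and reasons for missed doses. Whether it repeats the rule is not shown.
- No consequence for response or BTK occupancy is demonstrated, and the frequency of missed morning doses is unknown.

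These points limit the size of the problem. None removes the conflict in the text.

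**Conclusion.** The conflict is real and minor. For a missed morning dose on twice-daily acalabrutinib (starting dose, Level -2, and crossover subjects on either), the rule taken literally costs two doses and a nominal 36-hour gap, where the 12-hourly schedule would cost one dose and 24 hours. The rule gives the right result for a missed evening dose and for once-daily dosing at Level -1.

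This rests on the literal wording and on doses 12 hours apart; the choice of clock times does not matter. How often it would happen, and whether it would affect BTK occupancy or ORR, cannot be determined from the protocol. Sample size, error rates and the planned analyses are untouched.

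**What to change.** In Section 3.4.3, replace the reference to the scheduled time on the following day with: at its next regularly scheduled time (the same evening after a missed morning dose on a BID schedule). This wording remains correct for missed evening doses and for once-daily dosing. If the subject diary or dosing instructions repeat the rule, change them to match.

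The cost is one sentence in the protocol and any matching subject instruction, with no change to design, sample size or analysis.

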3.4.4 Assuring Subject Compliance

For treatments that are taken in the clinic, subjects should take the dose from the drug dispensed for them for that particular time period. All other acalabrutinib treatments will be taken at home. Subjects will receive a drug diary to record the specific time each dose was taken and to record reasons for any missed doses.

Pembrolizumab infusions will be administered only at the clinics per the study schedule. Missed doses of pembrolizumab should not be made up, with the next dose occurring in agreement with the original schedule for this agent (every 3 weeks).

Subject compliance with acalabrutinib dosing will be assessed at every visit. The subject will be instructed to bring the diary and any remaining capsules to the clinic at their next visit. The study staff will review the diary and ask the subject if all of the capsules were administered. Any remaining or returned capsules will be counted and recorded as described in [Section 7.6](#). Returned capsules must not be redispatched to another subject.

3.5 STUDY TREATMENT SCHEDULE

3.5.1 Arm 1 – Pembrolizumab Monotherapy

Pembrolizumab 200 mg will be administered every 3 weeks by IV infusion.

3.5.2 Arm 2 – Combination Treatment

The dose of acalabrutinib is 100 mg BID PO. The doses may be modified for DLTs as summarized in [Table 3-2](#).

Pembrolizumab 200 mg will be administered every 3 weeks by IV infusion for a maximum of 24 months from the date of first dose.

Acalabrutinib and pembrolizumab dosing will begin on the same day (Day 1 of Week 1) except for the first 6 subjects enrolled due to PK sampling. The first 6 subjects enrolled will receive acalabrutinib on Day 1 of Week 1. Then on Day 2 of Week 1 the first pembrolizumab infusion will be administered.

Table 3-2. Dose Reduction for Acalabrutinib

Dose Level	Acalabrutinib	Pembrolizumab
Starting Dose	100 mg BID PO	200 mg Q3W IV
Level -1	100 mg QD PO	200 mg Q3W IV
Level -2	50 mg BID PO	200 mg Q3W IV

Abbreviations: BID = twice per day; IV = intravenous, PO = oral; Q3W = every 3 weeks; QD = once per day

3.6 DURATION OF THERAPY

Subjects may continue to receive acalabrutinib treatment until disease progression or an unacceptable drug-related toxicity occurs as defined in the protocol. Pembrolizumab treatment is for 24 months from the date of first dose for subjects who are tolerating therapy and not progressing. Pembrolizumab treatment can end for subjects with confirmed CR if treatment has been administered for at least 24 weeks and 2 doses of pembrolizumab have been administered after confirmation of CR.

Treatment on this protocol can continue for a minimum of 12 months after the last subject is randomized to the study.

3.7 ASSESSMENT OF DOSE-LIMITING TOXICITY (DLT)

As outlined in [Section 3.0](#), DLT review will be applied to Arm 2 as the combination of acalabrutinib plus pembrolizumab has not been evaluated before, therefore an interim safety analysis will occur once 6 subjects have been successfully randomized to the combination arm (Arm 2) and have been treated a minimum of 4 weeks. Enrollment will be paused while the interim safety analysis occurs.

A DLT will be defined as the occurrence of any of the following study-drug-related AEs (note: AEs clearly related to disease progression or the subject's current medical history and associated comorbidities will not be considered DLTs):

1. Grade 4 vomiting or diarrhea
2. Grade 3 nausea, vomiting, or diarrhea lasting for > 72 hours
3. Other Grade ≥ 3 toxicities (Note: Transient Grade 3/4 laboratory abnormalities that are not clinically significant will not be considered DLTs)
4. Dosing delay due to toxicity for > 21 consecutive days.

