	
Although acalabrutinib has not demonstrated any dose-limiting toxicities (DLTs) to date, the safety of acalabrutinib in combination with pembrolizumab in this patient population needs to be assessed and standard DLT criteria will be applied to Arm 2 of the study. Therefore an interim safety analysis will occur once 6 subjects have been successfully randomized to the combination arm (Arm 2) and have been treated a minimum of 4 weeks. Enrollment will be paused while the interim safety analysis occurs. If a DLT rate of < 33% is observed in Arm 2 (ie, DLT review is cleared), then randomization will continue to evaluate the objective response rates of pembrolizumab monotherapy and the combination of pembrolizumab and acalabrutinib (ie, up to 37 total subjects per arm). If a DLT rate of $\geq 33\%$ is observed in Arm 2, then enrollment (1:1) will continue until an additional 6 subjects are randomized to Arm 2, but with a reduced dose level for acalabrutinib (Level -1). If the DLT review is cleared in those additional 6 subjects in Arm 2 then continued enrollment will occur at Level -1 for the combination arm. If a DLT rate of $\geq 33\%$ is observed in Arm 2 at Level -1, then an additional 6 subjects will be randomized at Level -2 and assessed for DLTs. If the DLT review is cleared, continued enrollment will occur at Level -2 for the combination arm. If the DLT review is not cleared, enrollment will be halted in Arm 2.
 
Acalabrutinib treatment can continue for subjects who are tolerating therapy and not progressing. Pembrolizumab treatment is for 24 months from the date of first dose for subjects who are tolerating therapy and not progressing. Subjects who have confirmed progressive disease on the combination of pembrolizumab and acalabrutinib will discontinue study treatment while those with confirmed progressive disease in the pembrolizumab monotherapy arm will continue on pembrolizumab with the addition of acalabrutinib until a second disease progression or intolerance to therapy. For subjects who cross over to receive combination treatment, acalabrutinib treatment will begin at the next visit at which subjects are scheduled to receive pembrolizumab. The immune-related response criteria (irRECIST; Appendix 8) will be used to determine progression on this study. Pembrolizumab treatment can end for subjects with confirmed complete response (CR) if treatment has been administered for at least 24 weeks and 2 doses of pembrolizumab have been administered after confirmation of CR.
 
Refer to Appendix 4 and Appendix 5 for comprehensive lists of study assessments and their timing. A study schema is provided in Figure 3-1.

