3.14 DATA AND SAFETY MONITORING

This trial will be monitored in accordance with the sponsor's pharmacovigilance procedures. Adverse events and SAEs will be reviewed internally on an ongoing basis to identify safety concerns. Quarterly conference calls with the investigators and applicable site staff will be conducted to discuss study progress, obtain investigator feedback and exchange, and discuss "significant safety events" (ie, AEs leading to dose reductions, related SAEs, and deaths). In addition, for the interim safety analysis, a mandatory safety teleconference will occur before the expansion phase of the protocol can open.

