5.0 STATISTICAL METHODS OF ANALYSIS

5.1 GENERAL CONSIDERATIONS

Descriptive statistics (including means, standard deviations, and medians for continuous variables and proportions and confidence intervals [CIs] for discrete variables) will be used to summarize data as appropriate.

For the interim safety analysis (DLT review), enrollment of 6 subjects in the combination arm for DLT review is consistent with sample sizes used in oncology studies for determination of MTD. The trial employs the standard National Cancer Institute definition of MTD (dose associated with DLT in $\leq 17\%$ of subjects). Provided the DLT review period is cleared in the combination arm and this arm is not stopped early for futility or toxicity ([Section 5.5](#)), then up to 31 subjects will be added per arm.

The sample size for this 2-arm trial was determined by a Z-test for normal approximation of binomial distribution, based on one-sided $\alpha = 0.10$, 80% power, with projected response rates of 40% in pembrolizumab/acalabrutinib arm and 18% in pembrolizumab

arm. [REDACTED] PASS version 11 was employed to conduct the sample size calculation.

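### At the starting dose, the enrolment pause is tied to the interim safety analysis rather than to the sixth Arm 2 randomisation, which conflicts with the protocol's own gates on expansion

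*Protocol*

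**What the plan says.** Section 3.7 and the Study Design part of the synopsis give the same trigger for the interim safety analysis: six subjects randomised to Arm 2 who "have been treated a minimum of 4 weeks". Both then add: "Enrollment will be paused while the interim safety analysis occurs". No other sentence says when enrolment stops at the starting dose.

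Four other places bear on the point:

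- **Synopsis, Study Design.** "If a DLT rate of < 33% is observed in Arm 2 (ie, DLT review is cleared), then randomization will continue", the ceiling being "up to 37 total subjects per arm". For Level -1, enrolment runs until six further subjects have been randomised to Arm 2, and continued enrolment depends on clearance in those six. For Level -2, six more are randomised and assessed, again with continued enrolment only if cleared.
- **Section 5.1.** Six combination-arm subjects make up the DLT review. If the DLT review period is cleared and the arm is not stopped for futility or toxicity, "then up to 31 subjects will be added per arm".
- **Section 3.14.** For the interim safety analysis, "a mandatory safety teleconference will occur before the expansion phase of the protocol can open".
- **Section 5.5 and Table 5-1.** Bayesian monitoring starts once ten Arm 2 subjects have been evaluated. The table gives no stopping count for one to nine subjects.

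**The concern.** A pause that lasts as long as the analysis starts when the analysis starts. The analysis cannot start until the sixth Arm 2 subject has had 4 weeks of treatment. A site or enrolment desk following the pause sentence alone would keep randomising 1:1 through that window. Subjects 7 onward in Arm 2 would then start a combination that Section 3.7 describes as not previously evaluated, at a dose the review may still reject.

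This is a patient-safety instruction, so it should have only one reading. Section 3.10.1 also warns that transaminase elevations may be more frequent and more severe with the combination. Any subjects 7 to 9 who entered early would have no formal stopping rule behind them until ten had been evaluated.

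**Working it through.** **1. The plan's own count.** Section 5.1 gives one-sided alpha 0.10, 80% power, and response rates of 40% and 18%. The unpooled Z formula gives

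n = (1.2816 + 0.8416)² × (0.18 × 0.82 + 0.40 × 0.60) / 0.22² = 4.508 × 0.3876 / 0.0484 = 36.1, rounded up to 37 per arm.

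The pooled version gives 38, and power at 37 on that version is 79.6%. So 37 reproduces, and 6 + 31 = 37 matches the split in Section 5.1. That split is exact only if Arm 2 holds six subjects at clearance, that is, if nobody beyond the DLT set enters during the window.

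**2. The passages side by side.**

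| Place | What it implies between the sixth randomisation and clearance |
|---|---|
| Section 3.7 and synopsis, pause sentence | Open until the analysis begins, at least 28 days after the sixth Arm 2 subject starts |
| Section 3.14 | Closed: expansion waits for the teleconference |
| Section 5.1 | Closed: the further 31 per arm wait for a cleared review period |
| Synopsis, Level -1 | Explicit count: six further Arm 2 subjects |

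**3. Size under the literal reading.** The protocol gives no accrual rate, so a range is assumed. With 1:1 allocation and a 28-day gap (the minimum), the expected number of extra Arm 2 subjects is (total accrual per month / 2) × 28 / 30.44. The chance of at least one uses a Poisson count with that mean.

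| Assumed total accrual per month | Expected extra Arm 2 subjects | Chance of at least one |
|---|---|---|
| 1 | 0.46 | 37% |
| 2 | 0.92 | 60% |
| 4 | 1.84 | 84% |
| 6 | 2.76 | 94% |
| 8 | 3.68 | 97% |

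**4. How often the review would reject the dose.** One DLT in six is 16.7% and clears. Two in six is 33.3% and does not. The probability of not clearing is 1 − (1 − p)⁶ − 6p(1 − p)⁵ for a true DLT rate p:

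- p = 0.20: 1 − 0.262 − 0.393 = 0.34
- p = 0.30: 1 − 0.118 − 0.303 = 0.58
- p = 0.40: 1 − 0.047 − 0.187 = 0.77

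Rejection is therefore a realistic outcome at plausible rates.

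**5. Other cover for subjects 7 to 9.** Recomputing the toxicity boundaries from the beta(0.3, 0.7) prior and the 0.90 cut-off reproduces Table 5-1 (6 of 10 to 12, 7 of 13 to 14, up to 15 of 35 to 36). The table is sound, but by design it is silent below ten subjects.

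**The case against.** The strongest reply is that the protocol, read as a whole, already holds at six. Section 5.1 makes the next 31 per arm conditional on a cleared review period, and the word period can be taken to include the observation time. Section 3.14 bars expansion before the teleconference, and a seventh Arm 2 subject who is not a replacement would belong to the expansion. Under Section 3.3.4 each site checks availability with the sponsor before screening, and the sponsor confirms each enrolment and issues the allocation, so sites cannot over-enrol on their own. Most of this stands. A hold at six is the likely intent, and the finding is conflicting text, not a permission to over-enrol. But Section 3.3.4 does not tell the sponsor to close slots at six, Section 3.14 attaches no subject number to the expansion phase, and the one sentence that mentions a pause starts it late.

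Two stronger readings are tempting, and the documents do not support them.

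- **Late entrants could dilute the DLT rate.** Because the clearance rule is worded as a rate in Arm 2, a reader might infer that two DLTs could pass as 2/7 = 28.6% instead of failing as 2/6 = 33.3%. Section 3.3.3 fixes the DLT assessment at N = 6, Section 5.1 says six subjects form the review, and Section 3.7 ties it to six subjects with at least 4 weeks of treatment. The denominator is six.
- **The same gap recurs at each lower level.** A reader might infer this from the shared procedure. The synopsis gives Level -1 an explicit count of six and both levels a clearance condition. What is missing there is only a stated hold while the review is in progress.

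**Conclusion.** The point holds as an internal conflict at the starting dose. The pause sentence, followed literally, leaves Arm 2 accrual open for at least 28 days before the DLT review, contrary to Sections 3.14 and 5.1 and out of step with the Level -1 wording. How many subjects this would affect is not determinable from the protocol. The range of about 0.5 to 3.7 extra Arm 2 subjects rests on an assumed total accrual of 1 to 8 per month, 1:1 allocation, a gap of exactly 28 days, and the literal reading being followed. The sponsor's control of slots could bring it to zero. The point does not affect the sample size calculation, the six-subject clearance rule or Table 5-1. It should be corrected because it concerns exposure to an uncleared combination.

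**What to change.** Reconcile the passages with one statement in Section 3.7, repeated in the synopsis. It should say that:

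- randomisation is held from the sixth Arm 2 randomisation;
- the only exception is replacements allowed under Section 3.3.3 to complete the DLT set;
- the hold ends when the DLT review is cleared at the Section 3.14 teleconference, or enrolment moves to the next level under the existing rules;
- the same hold point applies while Levels -1 and -2 are under review.

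No dose, DLT definition or clearance threshold needs to change. With the hold in place, no subjects beyond the DLT set start before clearance, and 6 + 31 = 37 is exact when the starting dose clears.

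The cost is amendment wording and about 4 to 5 weeks without randomisation per review: the 4-week window plus, by assumption, up to a week for the analysis and teleconference. Sections 3.14 and 5.1 already imply that delay.
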